Schematic illustrations are displayed in Figures 1-5. After consent, an esophageal catheter will be placed. The CDS tool for ventilator management will be placed at the bedside (on a laptop computer) for each enrolled patient, and recommendations regarding changing ventilator support will be provided to the clinicians every 2 hours or with a new arterial blood gas. Clinician decisions and changes to the ventilator with respect to each recommendation will be tracked. PEEP and FiO₂ management is based on current best evidence. Twice a day, transpulmonary pressure measurement will be obtained (a. on the current PEEP/FiO₂ combination- as recommended by the current best evidence and b. PEEP will be changed to make transpulmonary pressure zero). TPP measurements are obtained through an expiratory and inspiratory hold on the ventilator while the patient is not breathing significantly spontaneously. This methodology will be identical to what is already approved as part of another ongoing investigation at CHLA (CCI-13-00370). This data will be tracked to help generate a new protocol based on TPP. PEEP will be returned to the previous level after TPP calculations are complete. Once the patient meets criteria for spontaneous breathing (see flow diagram below, Figure 1), they will enter the effort of breathing weaning arm of the study.

In this weaning arm of the study, there will first be an oxygenation test to ensure the patient can tolerate lower levels of PEEP and FiO₂ in preparation for weaning. If they fail, they will go back to the previous ventilator settings and an oxygenation test will not be repeated again for 24 hours. If they pass, they will go to a 2 hour Spontaneous breathing trial. Esophageal manometry, spirometry, and Respiratory Inductance Plethysmography (RIP) bands will be in place. If they pass based on clinical criteria as well as guidance from the esophageal manometry protocol regarding effort of breathing and other pieces of extubation failure (such as direction of the Konno Meade plot as an indication of neuromuscular weakness) the recommendation will be to extubate. If the clinician elects not to extubate, the reasons will be tracked.

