2. Software pieces: Each patient should receive at least 24 recommendations on the CDS portion of the protocol and for those that fail the SBT, another 10-20 recommendations on the weaning protocol. We have migrated the CDS tool out of Microsoft Access, making it available in a web-browser to improve compatibility with clinical care. The rules of the protocol have not changed. The additional analysis will be to confirm that users can follow the new user interface. This should afford enough data to test the reliability of the software. From the 10-12 patients who are enrolled in the weaning protocol, at least 2 time points will be available to compare PRP values between the software tool and the post-processing program, allowing > 20 points for direct comparison.
3. Magnitude of reduction: It is anticipated that the expected duration of MV for those with anticipated lengths > 48 hours ranges from 5-7 days on average, with a wide range. While it is unlikely that we will have a definitive answer about the magnitude of effect, approximately 20 patients should provide data to get a reliable estimate of mean and standard deviation for length of ventilation to use in future calculations.
4. TPP separation: It is anticipated that 20 patients should yield a minimum of 60 TPP measurements (average 3/patient) which can be used to identify a potential separation between PEEP recommended by the protocol, and that which would be recommended by normalizing TPP. From the preliminary data we have to date (approximately 9 patients), there appears to be an average separation of 2 cmH₂O between clinician chosen PEEP and PEEP at TPP, although the variation is large. However, most of the time clinician chosen PEEP is below the evidence based recommendations. If we can demonstrate that for at least 50% of the observations (95% Confidence Interval 40-60%) there would be a separation of at least 2 cmH₂O, it would facilitate development of a protocol. To achieve this level of confidence, we would need a minimum of 50 observations.
5. NIV protocol: It is anticipated that 40% of patients who are extubated will be placed on NIV after extubation. This means that 10-12 patients will be left to test the protocol. Each patient should generate 10-20 recommendations on the NIV weaning protocol, giving approximately 100 recommendations to test.

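### The TPP separation criterion pools repeated observations with no allowance for clustering by child, so an interval that treats them as independent is too narrow and the pooled share can differ from the per-child share

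*Combined protocol and SAP*

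**What the plan says.** Section 6, Study Treatments, sets the schedule: "Twice a day, transpulmonary pressure measurement will be obtained". It then gives the condition: "TPP measurements are obtained through an expiratory and inspiratory hold on the ventilator while the patient is not breathing significantly spontaneously". The next stage begins "Once the patient meets criteria for spontaneous breathing", at which point the child enters the weaning arm. No cap or minimum number of TPP measurements per child is given.

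Section 7, item 4 (TPP separation) gives the expected yield: "It is anticipated that 20 patients should yield a minimum of 60 TPP measurements (average 3/patient". The benchmark, with separation measured in cmH₂O, is worded per observation: "If we can demonstrate that for at least 50% of the observations (95% Confidence Interval 40-60%) there would be a separation of at least 2". The plan describes the consequence of meeting this benchmark only in general terms: "it would facilitate development of a protocol". On precision it adds that "we would need a minimum of 50 observations".

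The outcome for this objective in Section 6, Study Outcomes, lists only the TPP values to be compared. Nowhere is there a rule for weighting by child, for correlation between measurements on the same child, or for children who yield none.

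**The concern.** Measurements repeated on one child are likely to resemble each other, so 60 observations from 20 children are not 60 independent pieces of information. An interval that ignores this is too narrow.

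The number of measurements per child is also not fixed by design. It depends on how long the child stays passive. The comparator PEEP comes from a PEEP/FiO₂ table, so oxygenation severity enters one half of the separation, and severity may also lengthen the passive phase. If the two are linked, the pooled share answers a different question from the share in the average child. A wider interval would not show that difference.

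At stake is the only stated benchmark for this objective. It is meant to inform a TPP protocol for a later randomized trial. A reader of the pilot could not tell whether 50% describes most children or mainly those measured most often.

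**Working it through.** **1. The plan's own figures.** The yield reproduces: 20 children × 3 = 60.

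The minimum of 50 does not. For a 95% interval of 40-60% around 50%, n = z²p(1−p)/d² = 1.96² × 0.25 / 0.10² = 96.04, so 97 independent observations.
- At n = 50 the half-width is 1.96 × √(0.25/50) = 0.139, an interval of 36-64%.
- At n = 60 it is 1.96 × √(0.25/60) = 0.127, an interval of 37-63%.
- A half-width of 0.10 at n = 50 corresponds to z = 0.10/√(0.25/50) = 1.414, roughly an 84% interval.

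The stated 50 is thus below the requirement even for independent observations, and clustering can only raise that requirement.

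**2. Effect of repeated measurements on precision.** Design effect = 1 + (Σm²/Σm − 1) × ICC, where m is the count per child. Effective n = 60/design effect. Half-width = 1.96 × √(0.25 × design effect/60). The documents give no ICC and no distribution of counts, so both are assumed.

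| Counts (20 children, 60 observations) | ICC | Design effect | Effective n | Half-width (points) |
|---|---|---|---|---|
| 3 each (Σm²/Σm = 180/60 = 3) | 0 | 1.0 | 60 | 12.7 |
| 3 each | 0.1 | 1.2 | 50 | 13.9 |
| 3 each | 0.3 | 1.6 | 37.5 | 16.0 |
| 3 each | 0.7 | 2.4 | 25 | 19.6 |
| 6×1, 6×2, 4×4, 2×6, 2×7 (264/60 = 4.4) | 0.1 | 1.34 | 44.8 | 14.6 |
| same uneven counts | 0.7 | 3.38 | 17.8 | 23.3 |

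Item 4 uses 20 patients although Section 7 requests 40. If all 40 gave 3 each (120 observations), the half-width would be about 9 points if independent and about 11 at an ICC of 0.3 (8.9 × √1.6 = 11.3).

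**3. Pooled share against per-child share.** Pooled = Σ(m × p)/Σm. Per-child = Σp/20. Here p is the share of a child's observations with the stated separation. All splits and rates are assumed; each row has 60 observations.

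| Fewer observations | More observations | Pooled | Per-child |
|---|---|---|---|
| 10 children × 1, p = 25% | 10 × 5, p = 60% | (2.5 + 30)/60 = 54.2% | 42.5% |
| 10 × 1, p = 60% | 10 × 5, p = 25% | (6 + 12.5)/60 = 30.8% | 42.5% |
| 10 × 2, p = 25% | 10 × 4, p = 60% | (5 + 24)/60 = 48.3% | 42.5% |
| 15 × 1, p = 40% | 5 × 9, p = 60% | (6 + 27)/60 = 55% | (6 + 3)/20 = 45% |
| 15 × 1, p = 60% | 5 × 9, p = 40% | (9 + 18)/60 = 45% | (9 + 2)/20 = 55% |
| any split, equal p | equal p | p | p |

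Both shares are weighted averages of the same two rates. They can straddle 50% only if the rates themselves lie on opposite sides of 50%. Even then they need not: rows 2 and 3 fall below 50% under both weightings. The shift can go in either direction.

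**The case against.** The strongest reply is that the pooled share is a legitimate target. A PEEP protocol acts at each assessment, and one based on ventilator holds could act only during passive ventilation, so the share of such assessments at which the two PEEP values differ is a sensible quantity. This stands. The per-child share is not the one right answer, and it has its own weakness: a child with one observation counts as much as a child with many. What is missing is a statement of which quantity is meant.

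A second reply is that the crossing of 50% rests on chosen rates, and that the 11.7-point gap in the first example is smaller than the 13-point half-width for 60 independent observations. The first part is true. The second does not dispose of the point, because the gap is between two targets and would remain with more children.

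A reader might go further and infer that a few of the most severely ill children dominate the result, or that case mix decides it. The documents do not support that: they give neither the distribution of passive time nor the counts per child. Nor can one infer from the average of 3 what fraction of twice-daily slots goes unmeasured. The yield and the number of recommendations are stated as minimums, recommendations also follow new blood gases, and TPP is described before the weaning arm, not across all of ventilation.

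Finally, this is one descriptive objective of a pilot. Meeting the benchmark would help protocol development; it is not a formal gate. This limits the consequence to a possibly misleading input to later work.

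**Conclusion.** The concern holds in a limited form. Item 4 judges a pooled share of repeated observations with no allowance for clustering, while Section 6 makes the count per child depend on passive time.

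The precision part needs only a positive correlation within children. Over the assumed ICC range, the half-width grows from about 13 points to 14-20 with equal counts, and further with uneven ones. The weighting part is conditional. It matters only if separation varies with passive time, and it changes the reading against 50% only if the rates lie on opposite sides of that value. The documents leave this open, so the direction and size of any difference are unknown.

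**What to change.** Amend Section 7, item 4 to:
- state that the pooled share describes assessments made during passive ventilation;
- compute its 95% interval with children as the clusters, by a cluster-robust method or a bootstrap over children;
- report beside it the equal-weight per-child share with its own interval;
- report the number of observations per child, including how many children contributed none;
- say that, if the two shares fall on opposite sides of 50%, this will be reported and the criterion will not be treated as clearly met.

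The minimum of 50 should be restated at the same time, since it does not give the quoted interval even under independence.

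No further patients or measurements are needed for this analysis. The cost is a wider interval and a little more analysis. Children without any observation still cannot enter the per-child share, which is why their number should be shown.

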If patients fail the SBT, they will be placed on the previous PEEP (prior to oxygenation test) and PS equal to the delta P (PIP-PEEP) on the previous ventilator support. The protocol will then make recommendations every 2 hours regarding weaning based on whether PRP has been in a range to wean, or a range to go back up on support (Figure 2). Clinicians will ultimately decide whether or not to accept these recommendations, and again reasons for rejection will be tracked. Once the patient achieves PS level of ≤ 8 cmH₂O, another SBT on CPAP will be recommended. If it has been 24 hours since the last SBT, regardless of PRP, another SBT will also be recommended. The clinician will chose whether or not to accept or reject the recommendation, and again reasons for rejection will be tracked. If the patient passes the SBT, the recommendation will be for extubation. If the patient fails the SBT, PS will be returned to its

previous level. No SBT recommendation will be made between 10pm-6am, so that extubation will take place at accepted times for extubation in our ICUs.

The PRP targets for weaning versus increasing support are based on analysis of the existing data from patients on PS and CPAP just prior to extubation, who were enrolled in the UAO study. From this data, over 90% of the patients who were extubated successfully had a PRP on PS < 250 , and a PRP on CPAP < 400 . Hence, the recommendations will be to wean PS if PRP is < 250 , to maintain PS if PRP is between 250 and 400, and to increase PS if PRP is > 400 . Ultimately, the clinician will make the final determination regarding whether or not to make the wean, or to extubate the patient.

The decision to begin non-invasive ventilation after extubation will be left to the clinician. NIV management will be per clinician choice, and we will not implement a NIV protocol.

Diaphragm ultrasound measurements will occur daily, and will be conducted by two providers who will remain blinded to each-other's measurements. We will place an ultrasound probe over the right hemi-diaphragm just lateral to the nipple line between and compute Diaphragm Contractile Activity (DCA). DCA is obtained by measuring the thickness of the right hemi diaphragm and calculating the percent difference between diaphragm thickness on inspiration and exhalation. We will also use ultrasound to measure diaphragm thickness on exhalation and monitor how this changes serially over time as a measure of the architecture of the diaphragm.

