[figure not shown]

Figure 1: High Level view of Flow Diagram of Study

Study Outcomes

The following study outcomes will be followed for each of the proposed study objectives.

1. **Objective:** To refine the esophageal manometry based effort of breathing weaning protocol so that it can be used easily, and can attain high protocol adherence for eventual use in a randomized controlled trial. **Outcome:** protocol adherence for each

Effort of breathing guided ventilator management for children: a pilot study

Protocol Version Date: March 2, 2021

recommendation, as well as qualitative data on the reasons for rejection of the recommendation. This will guide refinement of the protocol.

2. **Objective:** To demonstrate that integration of these two pieces of software together can be used safely to provide recommendations for ventilator management. **Outcome:** PRP values used to generate each recommendation will be tracked, and raw data will be recorded at least twice daily to compare calculated PRP values from the software program to the post-processing program we currently use for the UAO study. Will also track reasons for rejecting recommendations (above), specifically targeting any recommendations which were rejected because of perceived problems with the software or calculations (incorrect data etc).
3. **Objective:** To determine the potential magnitude of reduction in length of mechanical ventilation afforded by using such a weaning tool, to help determine estimated sample size for a future randomized controlled trial. **Outcomes:** The primary outcome is the total length of ventilation (invasive and non-invasive). Secondary outcomes include length of invasive ventilation, length of non-invasive ventilation, re-intubation rates, use of inhaled medications to treat UAO, use of steroids for UAO, post-extubation ICU length of stay. Sedation level will be tracked as this is a potential confounding variable, as well as fluid balance, details about endotracheal tubes, use of blood pressure medications, as well as procedures.

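### Objective 2 sets out to show safe use, but its outcomes test PRP values and clinician-detected faults, not whether recommendations were correct

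*Combined protocol and SAP*

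**What the plan says.** Objective 2 reads: "To demonstrate that integration of these two pieces of software together can be used safely to provide recommendations for ventilator management". Study Outcomes, item 2, gives it three measures:

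- Tracking: "PRP values used to generate each recommendation will be tracked".
- Agreement: "raw data will be recorded at least twice daily to compare calculated PRP values from the software program to the post-processing program".
- Rejections: reasons are recorded, "specifically targeting any recommendations which were rejected because of perceived problems with the software or calculations".

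Section 7, item 2, describes the matching analysis as confirming that users can follow the new web interface, testing the software's reliability, and comparing PRP at more than 20 points. It also says: "Each patient should receive at least 24 recommendations on the CDS portion". Patients who fail the spontaneous breathing trial get a further 10 to 20 weaning recommendations.

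Under Study Treatments, clinician decisions and ventilator changes are tracked for every recommendation, and PEEP and FiO₂ recommendations follow evidence-based rules. For weaning: "The protocol will then make recommendations every 2 hours regarding weaning based on whether PRP has been in a range to wean". Re-intubation is a secondary outcome of Objective 3, with follow-up to 48 hours after extubation (Study Termination).

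**The concern.** A safety claim about a recommending tool needs two things: how often it recommends wrongly, and what happens to patients when its advice is followed. The Objective 2 outcomes measure neither.

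The rejection measure finds a fault only when a clinician sees it and declines the advice. Objective 1 seeks high adherence, so a low count of software-related rejections cannot distinguish few faults from unnoticed ones. The PRP comparison is free of that selection, but it stops at the PRP value. A correct PRP fed into a wrongly applied rule would pass it, and so would a wrong ventilator or laboratory input to a recommendation that does not use PRP.

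The part without an independent check is also the part that changed. The CDS tool was moved from a desktop database to a web platform, and the effort-of-breathing rules, now with three ranges instead of two, sit inside it. The results are meant to prepare for a randomised trial of 300 to 700 patients per arm.

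**Working it through.** **Inputs.** From Section 7, items 1 and 2: 10 to 12 patients in the weaning protocol, at least 2 PRP time points each, 10 to 20 weaning recommendations each, and at least 24 CDS recommendations per patient. Sample size is 40, raised from 20. From Study Treatments: weaning recommendations every 2 hours, with PRP ranges divided at 250 and 400. From Study Outcomes: raw data at least twice daily. No margin, tolerable error rate or agreement limit is stated for Objective 2.

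**1. The plan's own figure.** 10 × 2 = 20 and 12 × 2 = 24 comparison points. This agrees with the stated figure of more than 20, apart from exactly 20 at the low end. The 10 to 12 patients fit a base of 20, since 60% × 20 = 12.

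**2. Coverage of weaning recommendations.**
- By the clock: 24 h / 2 h = 12 a day, and 2/12 = 17%. This takes each recording to coincide with one recommendation, which the text does not say.
- By Section 7's counts: recommendations run from 10 × 10 = 100 to 12 × 20 = 240. Coverage is 20/100 = 20% at 10 recommendations per patient and 24/240 = 10% at 20.
- With all 40 patients: 60% × 40 = 24 in weaning, 48 points, and 240 to 480 recommendations. The share is still 10% to 20%.

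**3. Coverage of all recommendations.** CDS recommendations number at least 24 × 20 = 480 in 20 patients, or 24 × 40 = 960 in 40. For 20 patients, PRP points reach between 20/(480 + 200) = 2.9% and 24/(480 + 120) = 4.0% of the total. This treats the 24 as separate from the PRP-based weaning recommendations, as Section 7 does.

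**4. Value against recommendation.** The middle range is 400 − 250 = 150 wide. Two PRP values inside it can differ by almost that much and give the same recommendation, while a small difference across 250 or 400 changes it. Agreement in PRP value therefore does not give the rate of changed recommendations.

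**5. What a clean result could show.** If each point were scored as same or different recommendation and none differed, the one-sided 95% upper limit would be 1 − 0.05^(1/n):

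| n | upper limit |
|---|---|
| 20 | 13.9% |
| 24 | 11.7% |
| 100 | 3.0% |
| 240 | 1.2% |

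These limits treat points as independent. Clustering within patients would generally widen them.

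**6. Objective against outcomes.** Tracking PRP records a value without judging it. The comparison tests the PRP calculation. Rejection reasons capture faults that clinicians noticed. None scores an accepted recommendation as right or wrong, and none is a patient event.

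**The case against.** The strongest reply is that the plan captures more than the rejection clause suggests. PRP and clinician decisions are logged for every recommendation, accepted ones included. The PRP comparison ignores the clinician's decision, so at a sampled time it can expose a wrong PRP behind accepted advice. An agreement study works from a sample, twice daily is a minimum, and a systematic calculation fault would probably show. The monitoring software has already been compared with post-processing in close to 400 patients. The CDS rules are viewable, were used in over 40 patients, and are said not to have changed on migration. The clinician makes every final decision.

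Most of this stands. A reader might infer that accepted errors fall wholly outside the outcomes; the PRP comparison shows that they do not. A reader might also want a count of missed errors, but the documents give neither an error rate nor a detection rate. Nor do they say that few software rejections will be taken as proof of safety. Returning a patient to previous support is a scheduled step after a failed oxygenation or breathing trial, so it should not be counted as harm.

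The reply leaves three gaps. Unchanged rules do not show that the new platform applies them correctly. Clinician discretion protects patients but does not measure safety. Logging accepted recommendations does not judge them.

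**Conclusion.** The outcomes listed for Objective 2 can support statements about PRP calculation agreement and usability. They cannot support the conclusion that the integrated software "can be used safely to provide recommendations for ventilator management". The independent check reaches 10% to 20% of weaning recommendations at the planned minimum and examines PRP values only. Recommendations that do not rest on PRP have no check in this pilot other than clinician rejection, and no patient event is named under the objective.

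The gap lies mainly in outcome definition and analysis, since most of the needed data are already planned. The coverage figures rest on Section 7's anticipated counts and on one recommendation per recording. Part of the document was not available, so safety monitoring described elsewhere cannot be excluded. The point concerns the stated outcomes. It does not invalidate the pilot, but it is worth correcting before the results are used to justify a trial.

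**What to change.** 1. At each planned raw-data recording, matched to a recommendation, re-derive the recommendation from the post-processed PRP using the protocol's own stated ranges. Report the proportion that differ from the one issued, split by accepted or rejected, with an interval that allows for clustering by patient.
2. Draw a random sample of CDS recommendations regardless of acceptance. Re-apply the tool's rules to the source ventilator and laboratory values, and report the proportion wrong, split the same way. The table above helps choose the sample size: 100 reviewed with none wrong gives an upper limit of 3.0% before allowing for clustering.
3. Report the re-intubations already collected within 48 hours after accepted extubation recommendations descriptively under Objective 2. Do not attribute cause, since there is no comparator.
4. If step 2 is not feasible because inputs are not kept, limit the Objective 2 conclusion to PRP calculation agreement and usability.

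The cost is modest data-management and analysis time, with no new patients or procedures. The one added requirement is that CDS inputs be retained or retrieved, because Methods of Data Collection does not say that they are archived.
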